### 7.3 For CLL patients with or without Richter's transformation (Arm A and Arm C), if a patient developed progressive disease (not tumor flare) at any time of the single-agent (MK-3475) therapy, or has stable disease without partial remission at the response

evaluation at month 3 of the single-agent (MK-3475) therapy, a commercially available FDA-approved CLL signal inhibitor can be added to MK-3475 (remain at the dose 200mg IV every 3 weeks). In this clinical scenario, if the patient had not used Ibrutinib in the past, Ibrutinib is recommended to be added using the standard FDA approved dose. However, the dose of Ibrutinib can be modified by treating physician based on concomitant medications or other clinical status. If the patient had progressed or had intolerable adverse events on Ibrutinib, Idelalisib is recommended to be added using the standard FDA approved dose. The dose of Ibrutinib or Idelalisib can be reduced/adjusted due to adverse events or concomitant medications according to the package inserts of the individual agent. If the patient had used both Ibrutinib and Idelalisib in the past, it is at the discretion of investigator/treating physician to decide which FDA-approved oral CLL therapy to use according to the package inserts of the individual agent and clinical status of the patient.

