11.1 Schedule of evaluations: For the purposes of this study, patients should be reevaluated for progression during each cycle assessment during the first 3 months of therapy with MK3475. After 3 months, patients who do not have evidence of PD or SD will continue on therapy and these patients will be evaluated for disease progression every other cycle. Formal response evaluation will occur at 3, 6, and 12 months since therapy start. For patients who discontinued the therapy due to adverse events, but have received at least 3 cycles of therapy and do not have evidence of PD, they should have formal response evaluation at about 2-8 weeks after the last dose of therapy or at the 3, 6, and 12-month time point since therapy start which ever occurs first. Prior to the first formal response evaluation, baseline on study measurements will be used to determine disease progression (e.g. not cycle by cycle comparisons). Once patients undergo formal response evaluation, the nadir value at either baseline or time of response evaluation will be used for evaluating future disease progression. In addition to a baseline scan, confirmatory scans should also be obtained as needed to document objective response at sites of non-palpable lymphadenopathy or organomegaly as indicated in Section 4 or as needed clinically.

NOTE: Information from CT scans is not considered in the standard classification of response.

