16.3 Analysis Plan (to be evaluated in each arm independently)

16.31 Primary Outcome Analyses:

16.311 Definition: The primary endpoint of this trial is the proportion of patients who achieve a confirmed response to single-agent MK-3475. A confirmed response is defined to be a PR, nPR, CCR, CRi or CR (Arms A and B) or PMR, CMR, PR or CR (Arm C) noted as the objective status at any time while on single-agent MK-3475. All patients meeting the eligibility criteria who have signed a consent form and have begun treatment will be evaluable for response, with the exception of patients determined to be a major violation. For CLL patients with Richter's transformation, confirmed response is determined by response criteria defined for Richter's transformation.

16.312 Estimation: In each arm, the proportion of successes will be estimated by the number of successes divided by the total number of evaluable patients in that arm. Exact binomial confidence intervals for the true success proportion will be calculated. In addition, the confirmed response rate for all Richter's transformation patients (9 patients from Arm A and all patients in Arm C) will be calculated.

16.32 Secondary Outcome Analyses (to be evaluated in each arm independently; Arm C analyses may include the 9 Richter's transformation patients from Arm A): (For all outcomes associated with combination therapy in Arms A and C, disease measurements obtained after the last cycle of single-agent therapy are set as the baseline measurements for combination therapy).

16.321 Progression-free survival (PFS) for single-agent MK-3475 is defined as

the time from registration to the earliest date of documentation of disease progression while on single-agent MK-3475 or death due to any cause. In Arm A and Arm C, patients who initiate combination therapy for stable disease after 3 months of single-agent MK-3475 will be censored on the date that combination therapy is initiated.

In Arm A and Arm C, PFS for the combination of MK-3475 and the signal inhibitor is defined as the time from initiation of treatment with the combination therapy to the earliest date of documentation of disease progression while on combination therapy or death due to any cause.

The distribution of progression-free survival will be estimated using the method of Kaplan-Meier.

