16.322 Treatment-free survival (TFS) for single-agent MK-3475 is defined as the time from registration to the date of initiation of subsequent treatment for CLL/SLL or lymphoma or death due to any cause. In Arm A and Arm C, the initiation of combination therapy with MK-3475 and the signal inhibitor will be considered subsequent treatment.

In Arm A and Arm C, TFS for the combination of MK-3475 and the signal inhibitor is defined as the time from initiation of combination therapy to the date of initiation of subsequent treatment for CLL/SLL or death due to any cause.

The distribution of treatment-free survival will be estimated using the method of Kaplan-Meier.

16.323 The time to next treatment (TNT) for single-agent MK-3475 is defined as the time from registration to the date of initiation of subsequent treatment for CLL/SLL or lymphoma. In Arm A and Arm C, the initiation of combination therapy with MK-3475 and the signal inhibitor will be considered subsequent treatment.

In Arm A and Arm C, TNT for the combination of MK-3475 and the signal inhibitor is defined as the time from initiation of combination therapy to the date of initiation of subsequent treatment for CLL/SLL.

The distribution of time to next treatment will be estimated using the method of Kaplan-Meier.

16.324 The complete response rate will be estimated by the number of patients who achieve a CRI or CR (Arms A and B) or CMR or CR (Arm C) divided by the total number of evaluable patients. Complete response rate will be evaluated for single-agent MK-3475 in each arm and also for the combination of MK-3475 and the signal inhibitor in Arm A and C. All evaluable patients will be used for this analysis. Exact binomial 95% confidence intervals for the true complete response rate will be calculated in each arm.

16.325 Duration of response (DR) is defined for all evaluable patients who have achieved a PR, nPR, CCR, CRI, or CR (Arms A and B) or PMR, CMR, PR or CR (Arm C) as the date at which the patient's objective status is first noted to be a PR, nPR, CCR, CRI, or CR (Arms A and B) or PMR, CMR, PR or CR (Arm C) to the earliest date relapse is documented. Duration of response will be evaluated for single-agent MK-3475 in each

arm and also for the combination of MK-3475 and the signal inhibitor in Arm A and C. The distribution of duration of response will be estimated using the method of Kaplan-Meier.

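### In Arms A and C, single-agent PFS is censored when an inhibitor is added for stable disease at month 3; this censoring is informative and can make the later Kaplan-Meier curve read too high

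*Combined protocol and SAP*

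**What the plan says.** Section 16.321 defines single-agent PFS as "the time from registration to the earliest date of documentation of disease progression while on single-agent MK-3475 or death due to any cause". For Arms A and C it adds that "patients who initiate combination therapy for stable disease after 3 months of single-agent MK-3475 will be censored", at the date the combination starts. The estimator follows: "The distribution of progression-free survival will be estimated using the method of Kaplan-Meier". Section 16.3 gives no sensitivity analysis, competing-risk analysis or second PFS definition.

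Section 7.3, repeated in 13.1, says who may switch. A patient who progresses at any time on single agent, or who "has stable disease without partial remission" at the month-3 evaluation, qualifies, and then "a commercially available FDA-approved CLL signal inhibitor can be added to MK-3475". Patients who switch for progression already have a PFS event, so the censoring rule removes only those with stable disease. Section 11.1 goes further on who stays: "After 3 months, patients who do not have evidence of PD or SD will continue on therapy".

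The neighbouring endpoints treat the same act differently. For TFS (16.322) and TNT (16.323) in Arms A and C, "the initiation of combination therapy with MK-3475 and the signal inhibitor will be considered subsequent treatment", which makes it an event.

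**The concern.** Kaplan-Meier is valid under censoring only if the patients removed have the same future risk as those who remain. Here the protocol selects the removed patients by their month-3 result: stable disease may leave the risk set, response does not. From that point the curve gives the removed patients the hazard of a risk set enriched for responders.

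Single-agent PFS is a named secondary goal (2.22), and it enters the Cox models against PD-1, PD-L1 and PD-L2 (16.331), which inherit the same response-dependent censoring. Arm B has no combination phase and no such rule. Figures labelled single-agent PFS would therefore rest on different censoring in different arms.

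**Working it through.** **The plan's own figures.** The documents state no PFS median, rate or event count. The only stated operating characteristics belong to the response rules, and exact binomial tails reproduce them. Five or more of 23 gives 0.0731 at a 10% response rate and 0.8644 at 30% (stated 0.07 and 0.86). Five or more of 17 gives 0.0987 at 15% and 0.8740 at 40% (stated 0.10 and 0.87). None of these depends on PFS.

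**Illustrative inputs, all assumed.** At month 3: 35% progressed or dead, 40% stable (D = 0.40), 25% responding (R = 0.25). After month 3, exponential times on single agent with median 12 months for responders and 4 months for stable patients. A fraction f of stable patients adds an inhibitor at month 3.

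Survival from month 3 to month 9 is r = 2^(-6/12) = 0.707 for responders and s = 2^(-6/4) = 0.354 for stable patients.

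- PFS at 9 months had everyone continued single agent: R·r + D·s = 0.25 × 0.707 + 0.40 × 0.354 = 0.177 + 0.141 = 0.318.
- Planned Kaplan-Meier (large-sample value): 0.65 × [R·r + D(1−f)·s] / [R + D(1−f)].
- Proportion still progression-free on single agent: R·r + D(1−f)·s.

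| Uptake f | Responders' share of risk set after month 3 | Kaplan-Meier at 9 months | Excess over 31.8% | Still progression-free on single agent |
|---|---|---|---|---|
| 100% | 100% | 46.0% | +14.1 points | 17.7% |
| 75% | 0.25/0.35 = 71% | 39.4% | +7.6 | 21.2% |
| 50% | 0.25/0.45 = 56% | 35.7% | +3.9 | 24.7% |
| 25% | 0.25/0.55 = 45% | 33.4% | +1.6 | 28.3% |

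**Median.** Had all continued, 0.25 × 2^(-t/12) + 0.40 × 2^(-t/4) = 0.5 gives t = 2.1, a median of 5.1 months. At full uptake, 0.65 × 2^(-t/12) = 0.5 gives t = 4.5, a reported median of 7.5 months. If half or more of the arm fails before month 3, the curve crosses 50% before any of this censoring and the median does not move.

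**Other assumptions.** The grid had response 10–40%, early failure 20–40%, responder median 18 months, stable-disease median 3 or 6 months, and uptake 50–100%. The planned 12-month estimate exceeded the continued-single-agent value in every scenario, by about 3 to 41 points. With the stable-disease median also set to 18 months the excess was zero.

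**At the trial's sample sizes.** These simulations assumed 30% early failure, later medians of 18 months (responders) and 6 months (stable), and full uptake. With n = 23 and 30% response, mean 12-month PFS was 0.49 as planned against 0.35 had all continued. With n = 17 and 40% response it was 0.49 against 0.39. In both, about 7 patients remained at risk after month 3.

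**The case against.** **Uptake is unknown.** The switch is optional. The notes to the single-agent test schedule (4.1) and Section 7.2 foresee responsive or stable patients still on treatment after 6 months, and 13.3 continues those not progressing. Section 11.1 points the other way. Section 7.2 covers all three arms, so its stable patients may include Arm B's. These passages should be reconciled, but as they stand they do not fix how many stable patients leave. This stands, and it limits the size of the bias. A reader might infer that the curve after month 3 rests mainly on responders. That is true at high uptake, but at 25% uptake in the base case responders are 45% of the risk set.

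**Direction is assumed.** The documents do not say that stable patients would progress sooner than responders. It is plausible, and without it the upward bias disappears.

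**TFS and TNT already count the switch.** They do, and the censoring rule is prespecified and open. TFS is close to a time-to-single-agent-failure measure. However, it does not count progression without new treatment, and it leaves the PFS curve as it is.

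**Counting the switch as failure overcorrects.** In the base case at full uptake it gives 18%, against 32% had all continued and 46% by Kaplan-Meier. It misses by the same 14 points in the other direction because it answers another question. This stands, and it is why the alternative belongs beside the planned curve and should not replace it.

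**Consequence is limited.** PFS is secondary and descriptive, with no test, threshold or sample size attached.

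**Conclusion.** The concern holds for Arms A and C. The censoring is triggered by lack of response, so it is informative by design, and nothing in 16.3 addresses it. The upward direction rests on stable patients progressing sooner than responders. The size rests on later hazards and uptake, which the documents do not give. In the assumed base case the 9-month excess is about 14, 8 and 4 points at 100%, 75% and 50% uptake.

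Two stronger readings are not supported. A reader might infer that the median and every later estimate must be too high; the median is affected only if fewer than half of the arm fail before month 3. A reader might also infer that the bias grows as the drug becomes less active. At full uptake the excess is D × (r − s), so moving patients from stable disease to early progression shrinks it: 0.25 × 0.354 = 8.8 points with 60% early failure and 25% stable, and 0.20 × 0.354 = 7.1 points with 70% and 20%.

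The primary response rule, the sample size and Arm B are unaffected. This is a change that should be made, not a flaw in the trial's main conclusion.

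**What to change.** Amend 16.321 for Arms A and C as follows:

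- Keep the planned Kaplan-Meier curve. Beside it, add a competing-event analysis: Aalen-Johansen cumulative incidence of progression or death on single agent, and of adding an inhibitor for stable disease.
- Give the proportion still progression-free on single agent at 3, 6 and 12 months. State that it is a different estimand (time to single-agent failure) and a lower bound for PFS had single agent continued.
- Report the number censored for stable disease and the numbers at risk after month 3.
- Show TFS beside PFS.
- Label Kaplan-Meier estimates beyond month 3, and any median that falls there, as assuming non-informative censoring.

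The cost is a few lines of plan text, slightly more analysis with standard software, and a companion figure less favourable than the planned curve. No patient's treatment or assessment changes.

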**5.0 Grouping Factor:**

5.1 Treatment Arm: Arm A (CLL/SLL and CLL with Richter's transformation) vs Arm B (low grade NHL) vs. Arm C (CLL with Richter's transformation)

Note: CLL patients with Richter's transformation or Hodgkin's transformation will be included in Arm A and C.

As per MCCC Addendum 2: An arm (Arm C) with CLL patients with Richter's transformation only is added to the study.

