- An unacceptable adverse event that occurs after the patient received at least 2 cycles of treatment, which in the opinion of the Investigator, precludes further trial participation.

13.5 Event Monitoring: Patients will enter event monitoring for the following reasons:

- If the patient develops evidence of PMD/PD (For CLL Arm A and C: PMD/PD on combination therapy; For B-NHL Arm B: PD on MK-3475 single therapy) during treatment or OBSERVATION by examination, blood counts, or imaging as defined in Sections 11.23, 11.4, 11.54 and 11.61, they will be considered to have progressed and will enter EVENT MONITORING. Refer to Section 4.0 for required tests at PMD/PD.

NOTE: Patients whose only evidence of disease recurrence is by sensitive evaluation of MRD will continue under OBSERVATION in accord with standard clinical practice and will NOT be considered PD.

- Subsequent treatment for CLL or NHL
- Failure to return for an evaluation during OBSERVATION
- Patient refusal of further study treatment or noncompliance
- Patient develops an intercurrent illness that precludes further participation, or requires a prohibited concomitant treatment
- The Investigator withdraws the patient in the patient's best interests
- Administrative reasons (e.g., the patient is transferred to hospice care)
- Pregnancy
- An unacceptable adverse event that occurs during cycles 1-2

**Note:** When a subject discontinues treatment, all applicable activities scheduled for the final trial visit should be performed at the time of discontinuation. Any adverse events which are present at the time of discontinuation/withdrawal should be followed in accordance with the safety requirements outlined in Section 10.0 -Assessing and Recording Adverse Events

13.6 A patient is deemed ineligible if after registration, it is determined that at the time of registration, the patient did not satisfy each and every eligibility criteria for study entry. The patient will go directly to the event-monitoring phase of the study:

- If the patient received treatment, all data up until the point of confirmation of ineligibility must be submitted. Event monitoring will be required per Section 18.0 of the protocol.
- If the patient never received treatment, on-study material and the End of Active Treatment/Cancel Notification Form must be submitted. No further data submission is necessary.

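### For the combination, TFS and TNT count later treatment for CLL/SLL but omit lymphoma, so therapy for Richter's or Hodgkin transformation may not count as an event

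*Combined protocol and SAP*

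**What the plan says.** Goal 2.25 names treatment-free survival and time to next therapy on the combination as secondary aims in Arms A and C. Section 16.3 gives each endpoint two definitions.

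- **TFS, single agent (16.322):** "the time from registration to the date of initiation of subsequent treatment for CLL/SLL or lymphoma or death due to any cause".
- **TFS, combination (16.322):** "from initiation of combination therapy to the date of initiation of subsequent treatment for CLL/SLL or death due to any cause".
- **TNT, single agent (16.323):** "the time from registration to the date of initiation of subsequent treatment for CLL/SLL or lymphoma".
- **TNT, combination (16.323):** "the time from initiation of combination therapy to the date of initiation of subsequent treatment for CLL/SLL".

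All four are to be estimated by Kaplan-Meier. On who receives the combination, Section 5.0 says: "An arm (Arm C) with CLL patients with Richter's transformation only is added to the study". Section 16.23 counts 9 Richter's patients in Arm A, and Section 16.32 allows them to be pooled into the Arm C secondary analyses. Section 13.5 lists "Subsequent treatment for CLL or NHL" among the reasons for entering event monitoring.

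**The concern.** The reference to lymphoma disappears from exactly the two definitions that apply to the arms containing transformed disease. Elsewhere the protocol treats that disease as lymphoma. Section 11.0 separates its lymphoma phase from the CLL phase and assesses the two by different criteria. Section 11.6 applies the Lugano lymphoma criteria. The note opening Section 13.0 ties treatment and follow-up decisions to the Richter's criteria.

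A programmer who follows 16.322 and 16.323 to the letter would not count lymphoma-directed therapy given after the combination. Another might code the same therapy as CLL treatment. The two would report different TFS and TNT from the same data. If combination TNT enters the biomarker Cox models of Section 16.331, which list TNT without saying which version is meant, the discrepancy carries over.

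**Working it through.** **No plan figure to reproduce.** The documents give no median, rate or event count for TFS or TNT. The only design figures are the response-rate tables in 16.22 and 16.24. Exact binomial tails reproduce them: 5 or more of 23 has probability 0.073 at a true rate of 10% and 0.864 at 30% (stated 0.07 and 0.86); 5 or more of 17 has 0.099 at 15% and 0.874 at 40% (stated 0.10 and 0.87). None of these involves TFS or TNT.

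**Events, side by side.**

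| Endpoint | CLL/SLL therapy | Lymphoma therapy | Death |
|---|---|---|---|
| TFS, single agent | event | event | event |
| TFS, combination | event | not named | event |
| TNT, single agent | event | event | not an event |
| TNT, combination | event | not named | not an event |

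**Direction.** Take a patient who starts the combination at time 0, receives lymphoma-directed therapy at time T and dies at D > T without CLL/SLL therapy.

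- With lymphoma counted, TFS = T and TNT = T, both events.
- Read literally, TFS = D, and there is no TNT event.

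A patient's event time is therefore the same or later, never earlier. TFS is capped by death; TNT is not.

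**Who can be affected.** Richter's patients number 9 in Arm A and 17 evaluable (20 accrued) in Arm C, so 9 + 17 = 26 to 9 + 20 = 29 at the very most. Sections 7.3 and 13.1 allow the inhibitor only after progression on single-agent therapy or for stable disease at month 3, so the true number is whatever subset starts it; the documents do not give it. Arm A patients with Hodgkin transformation, or who transform on study, would add to it.

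**Illustration only; every input is assumed.** Exponential times; median 6 months to next therapy; median 24 months to death without it; median 6 or 12 months to death after it; cut at 48 months (Section 18.1 ends follow-up four years after registration); no CLL/SLL therapy after lymphoma therapy; patients remain at risk until death or the cut.

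With lymphoma counted, median TFS is 1/(1/6 + 1/24) = 4.8 months and median TNT is 6.0 months. Simulated medians under the literal wording are below; each range spans the two post-therapy survival assumptions.

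| Share of next therapies given for lymphoma | TFS, months | TNT, months |
|---|---|---|
| 25% | 6.0–6.3 | 9.1–9.4 |
| 50% | 7.5–8.6 | 18.5–24.2 |
| 75% | 9.4–12.0 | not reached |
| 100% | 11.3–15.9 | no events |

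The result also depends on a censoring rule that 16.323 does not give. If patients were instead censored at lymphoma therapy, constant hazards would multiply median TNT by 1/(1 − s), where s is the lymphoma share. At s = 50% that is 2.0, or 12 months, against 18.5–24.2 above. Only the direction is robust.

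**The case against.** The wording has an ordinary explanation. The single-agent definitions serve all three arms, and Arm B is lymphoma, so they need the word. The combination definitions serve only the CLL arms, and the protocol often files transformed disease under CLL. Section 16.1 includes it in its description of the CLL/SLL population, Sections 1.6 and 1.7 justify the combination for relapsed CLL with Richter's included, and Section 12.1 lists both transformations as descriptive factors of CLL patients. On that reading, therapy for Richter's is therapy for CLL/SLL and already counts. The Section 13.5 item may simply name the two disease groups, and the follow-up form in Section 18.1 records subsequent treatment without a disease qualifier.

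This stands as far as it goes: it makes the bias conditional on coding. It does not settle the coding. No section says that therapy for transformed disease counts as CLL/SLL treatment, and Sections 11.0 and 11.6 point the other way.

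Three stronger inferences are tempting and are not supported:

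- **All of Arm C is affected.** Single-agent responders who do not progress never start the combination. Nor do the documents say what the next therapy after the combination will mostly be directed at.
- **The mismatch makes the combination look better than single-agent MK-3475.** Section 16.3 plans no such comparison. The clocks start at different points, and starting the combination is itself a single-agent TFS and TNT event. The two were never like for like, and the fix would not make them so.
- **The inflation can be stated as a multiplier.** The lymphoma share, the hazards and the censoring rule are all missing from the documents.

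**Conclusion.** The mismatch is certain and can be read directly from 16.322 and 16.323. Its effect is conditional: if therapy for Richter's or Hodgkin transformation is not coded as CLL/SLL treatment, TFS and TNT on the combination can only be lengthened, TNT more than TFS. The size cannot be derived from the documents, and the illustration shows direction, not a prediction.

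The reach is limited to patients who start the combination and then receive therapy recorded as being for lymphoma. Both endpoints are secondary and descriptive. The primary response rate, the decision rules for all three arms and combination PFS, which captures progression separately, are unaffected. The text should still be corrected, because Goal 2.25 names these endpoints for an arm made up only of transformed disease.

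**What to change.** In the combination definitions of both 16.322 and 16.323, end the interval at *subsequent treatment for CLL/SLL or lymphoma (including Richter's or Hodgkin transformation)*, and apply this in Arms A and C. TFS keeps death as an event; TNT is otherwise unchanged.

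The cost is one phrase in two definitions. Sections 13.5 and 18.1 already capture subsequent treatment in event monitoring, so no new collection should be needed. The change also spares the analyst from having to decide whether a given therapy was for CLL or for its transformation. The only downside is that reported TFS and TNT on the combination may be shorter.

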## 1.0 Background

### 1.1 Overview of Chronic Lymphocytic Leukemia (CLL)

Approximately 16,000 new CLL cases are diagnosed annually and ~100,000 patients are currently alive with CLL disease in the United States. Approximately 70% CLL patients eventually progress to require treatment and a majority of these patients will ultimately die from CLL or CLL related complications. Except limited patients who underwent allogeneic stem cell transplant and achieved long term remission, CLL is an incurable disease. Chemoimmunotherapy (CIT), typically as a combination of a purine analog, cyclophosphamide and rituximab, is very effective and has been established as the front-line therapy for CLL. However, majority of treated patients will relapse. Therapies for the relapsed CLL patients are evolving. Bendamustine and rituximab combination therapies have emerged as one of the effective approaches for relapsed patients. However, only about 10% of patients achieve a complete remission and around 60% overall response rate can be achieved with this approach. Progression free survival (PFS) is typically short in the range of 1-2 years (Fischer, Cramer et al. 2011).

In the last 5 years, significant advancements have been made in the understanding of importance of B-cell receptor (BCR) signal pathway in CLL disease as well as in other B-cell lymphoma. Agents targeting BCR pathway, specifically Bruton's Tyrosine Kinase (BTK) inhibitor Ibrutinib and PI3K inhibitor Idelalisib, have been observed to achieve approximately 70% overall response rate in relapsed/refractory CLL (Byrd, Furman et al. 2013). Ibrutinib has been FDA approved for previous treated CLL patients. The longest follow-up data on Ibrutinib showed about 40-50% CLL patients relapsed after about 2.5 to 3 years of Ibrutinib treatment. CLL relapse after Ibrutinib therapy has been observed and how to manage relapsed CLL patients after Ibrutinib therapy is unknown.

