## Follow-up Material(s)

CRF	Event Monitoring Phase 				
	q. 6 months until PMD/PD or subsequent treatment	At PMD/PD or subsequent treatment	q. 12 mos. after PMD/PD or subsequent treatment	Death	New Primary
Event Monitoring	X 	X 	X	X	At each occurrence

1. If a patient is still alive 4 years after registration, no further follow-up is required.
2. Submit copy of documentation of response or progression to the MCCC Operations Office, Attention:   
[REDACTED].

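### Time to next treatment leaves death out of the event but is estimated by Kaplan-Meier, so 1 − KM overstates the proportion who start next therapy

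*Combined protocol and SAP*

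**What the plan says.** Time to next therapy is a secondary goal for the single agent in all three arms (Section 2.22) and for the combination in Arms A and C (Section 2.25).

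Section 16.323 gives the definitions. For the first phase, "time to next treatment (TNT) for single-agent MK-3475 is defined as the time from registration to the date of initiation of subsequent treatment". In the second phase, "TNT for the combination of MK-3475 and the signal inhibitor is defined as the time from initiation of combination therapy to the date of initiation". The event there is later therapy for CLL/SLL. Neither definition mentions death. The section closes with the estimator: "The distribution of time to next treatment will be estimated using the method of Kaplan-Meier".

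Section 16.322 defines treatment-free survival (TFS) from the same starting points and with the same treatment event, but it adds death. The single-agent endpoint there is the "date of initiation of subsequent treatment for CLL/SLL or lymphoma or death due to any cause", and the combination version also counts death. Death is therefore exactly what separates TFS from TNT.

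For single-agent TFS and TNT in Arms A and C, the plan adds that "the initiation of combination therapy with MK-3475 and the signal inhibitor will be considered subsequent treatment".

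No section says how a death before next treatment is handled in TNT. Neither competing risks nor cumulative incidence is mentioned. TNT is also used in the Cox models for biomarkers in Section 16.331.

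**The concern.** A patient who dies without further therapy can never start it. If that patient is censored at death, Kaplan-Meier treats him or her as someone who would have gone on to start treatment at the same rate as those still alive and untreated. The resulting curve describes a setting in which nobody dies first. Read as a proportion, 1 − KM is too high, and the time at which half the patients appear to have started next therapy is too early.

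Deaths before next therapy are plausible here. Section 3.19e admits patients who have failed, cannot tolerate or have refused other approved effective therapies. Section 13.5 foresees transfer to hospice care. Section 1.1 says of CLL patients who come to need treatment that "a majority of these patients will ultimately die from CLL or CLL related complications". None of this gives a rate.

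What is at stake is how a secondary endpoint is read. Section 16.6 commits the secondary endpoints to public reporting, and a reader of a TNT curve will naturally take it as the share who needed another treatment.

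**Working it through.** The plan states no expected rate, sample size or power for TNT, so there is no figure of its own to reproduce. The check has two parts.

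**Direction (no assumed rates).** At each treatment start, let d/Y be the number starting divided by the number at risk.

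- Kaplan-Meier with deaths censored: 1 − KM = Σ S_KM(t−) × d/Y, where S_KM drops only at treatment starts.
- Aalen-Johansen: CIF = Σ S_TFS(t−) × d/Y, where S_TFS drops at treatment starts and at deaths.

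The terms d/Y are identical, and S_TFS is never above S_KM. So 1 − KM is never below the cumulative incidence, and it is strictly above it once a death without treatment is followed by another patient's treatment start. With no such deaths the two are equal.

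**Size (assumed rates).** Inputs:

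- Median time to next treatment if nobody died: 12 months (assumed; 6 and 24 also tried).
- Death hazard as a multiple r of the treatment hazard: 0 to 1.0 (assumed).
- Constant hazards: λt = ln 2 / median, λd = r × λt.
- Longest horizon: 48 months, from Section 18.1 (Follow-up Materials): "If a patient is still alive 4 years after registration, no further follow-up is required".

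Formulas: 1 − KM = 1 − exp(−λt T); CIF = λt/(λt + λd) × [1 − exp(−(λt + λd)T)].

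With a 12-month median and T = 24, exp(−λt T) = 2^(−2) = 0.25, so 1 − KM = 75.0% whatever r is. For r = 0.5, CIF = (1/1.5) × (1 − 2^(−3)) = 0.6667 × 0.875 = 58.3%. All cases at 24 months:

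| r | 1 − KM | Cumulative incidence | Excess (points) |
|---|---|---|---|
| 0 | 75.0% | 75.0% | 0 |
| 0.1 | 75.0% | 71.1% | 3.9 |
| 0.25 | 75.0% | 65.9% | 9.1 |
| 0.5 | 75.0% | 58.3% | 16.7 |
| 1.0 | 75.0% | 46.9% | 28.1 |

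At 48 months 1 − KM is 93.8%, against 86.6%, 77.5%, 65.6% or 49.8% for r = 0.1, 0.25, 0.5 or 1.0.

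The median moves as well. Kaplan-Meier gives 12 months in every row. The cumulative incidence reaches 50% at t = 12 × log2[1/(1 − 0.5(1 + r))]/(1 + r). That is 12.6 months for r = 0.1, 13.6 for r = 0.25 and 16.0 for r = 0.5. For r = 1.0 it is never reached.

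Over the whole assumed grid (median 6, 12 or 24 months, r from 0.1 to 1.0) the excess is 0.5 to 28.1 points at 12 months, 1.5 to 43.9 at 24 months and 3.9 to 49.6 at 48 months.

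**At trial size.** Simulation (4,000 runs, 12-month median, r = 0.5, horizon 24 months) gave a mean 1 − KM of 74.8% with 17 patients and 75.1% with 23. The proportions actually starting treatment were 58.3% and 58.4%. Small arms do not remove the gap.

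**The case against.** Several points on the other side stand in whole or in part.

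- **The plan promises a time distribution, not a share treated.** With deaths censored, the Kaplan-Meier curve is a legitimate summary of the rate of starting treatment among patients still alive and untreated. A reader might infer that the curve and its median are simply wrong. The narrower statement is right: they cannot be read as the proportion treated, or as the time by which half were treated.
- **Censoring at death is not written out.** A reader might infer that the plan instructs it. It does not. It is the default that follows from the definition and the method, and the contrast with TFS makes it the natural reading.
- **TFS and overall survival are reported alongside.** This limits how far a reader can be misled. But TFS merges death with treatment, and neither endpoint yields the share who start next therapy.
- **In Arms A and C, adding the inhibitor is the single-agent event.** Sections 7.3 and 13.1 allow it at progression or for stable disease at month 3, so many events may come early and leave few deaths ahead of them. This probably reduces the gap there. It does nothing for combination TNT, or for Arm B, which has no combination phase.
- **The arms are small.** With 17 patients, a 95% interval around 60% is roughly ±1.96 × √(0.6 × 0.4/17) = ±23 points. That limits any conclusion, but an interval around the wrong quantity does not show the bias.
- **Low death rates give a small gap.** At r = 0.1 with a 12-month median it is 3.9 points at 24 months, and nothing in the documents rules that out.

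**Conclusion.** The point holds as a matter of method. Under the definition and estimator in Section 16.323, 1 − KM for TNT overstates the proportion who start next therapy if any patient dies untreated before others start. The direction needs no assumption beyond default censoring at death. The size does: the documents give neither a treatment rate nor a death rate, so the figures above are illustrations and the whole range should be kept in view.

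Three stronger readings are not supported:

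- A reader might expect the problem to be worst in Richter's patients because they die early. The documents give no survival figure for them, and the statement in Section 1.1 concerns eventual death from CLL, not death before next therapy.
- A reader might count the TFS sentence, "The distribution of treatment-free survival will be estimated using the method of Kaplan-Meier", as a second instance. It is not: TFS includes death, so Kaplan-Meier is appropriate there.
- A reader might think that the trial's conclusions are at risk. The decision rules in Sections 16.21 and 16.23 rest on response alone, TNT is secondary and descriptive with no decision rule attached, and the Cox models in Section 16.331 remain valid when read as cause-specific hazards.

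**What to change.** In Section 16.323, state how death is handled and replace the estimator for both phases. For example: the cumulative incidence of subsequent treatment will be estimated by the Aalen-Johansen method, with death without subsequent treatment as a competing event; patients alive without subsequent treatment will be censored at last contact. Showing the cumulative incidence of death without subsequent treatment beside it would let the two curves add up to 1 − TFS. Leave Section 16.322 as it is. In Section 16.331, add that hazard ratios for TNT are cause-specific.

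The cost is two or three sentences and a standard procedure. No new data are needed: the event-monitoring schedule in Section 18.1 already covers both subsequent treatment and death.
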